6.2 IMPORTANT PROTOCOL DEVIATIONS

Data discrepancies and deviations from the CTP will be identified for all treated subjects.

Consistency check listings (for identification of deviations of time windows) and a list of protocol deviations (e.g. deviations in drug administration, in blood sampling times, etc.) will be provided to be discussed at the Report Planning Meeting (RPM). At this meeting, all manual deviations identified at the sites by the CRAs and deviations too complex to program will be reviewed by the trial team to decide which are considered important. For definition of important protocol deviations (iPD), and for the process of identification of these, refer to the Boehringer Ingelheim (BI) SOP "Identify and Manage Important Protocol Deviations (iPD)" (2).

Section 7.3 of the CTP: *Important protocol deviation (iPD) categories will be suggested in the iPD specification file, iPDs will be identified no later than in the Report Planning Meeting, and the iPD categories will be updated as needed.*

If any iPDs are identified, they are to be summarised into categories and will be captured in the iPD specification file and the decision log. The iPD specification file (e.g. the DV domain specifications) will be stored within the TMF in EDMS.

The iPDS will be summarized and listed in the CTR.

6.3 SUBJECT SETS ANALYSED

Section 7.3 of the CTP:

- *Treated set (TS): The treated set includes all subjects who were randomized and treated with at least one dose of study drug. The treated set will be used for safety analyses.*
- *Pharmacokinetic parameter analysis set (PKS): This set includes all subjects in the treated set (TS) who provide at least one PK endpoint that was defined as primary or secondary and was not excluded due to a protocol violation relevant to the evaluation of PK or due to PK non-evaluability (as specified in the following subsection 'Pharmacokinetics'). Thus, a subject will be included in the PKS, even if he/she contributes only one PK parameter value for one period to the statistical assessment. Descriptive and model based analyses of PK parameters will be based on the PKS.*

[...]

Plasma concentration data and parameters of a subject will be included in the statistical pharmacokinetic (PK) analyses if they are not flagged for exclusion due to a protocol deviation relevant to the evaluation of PK (to be decided no later than in the Report Planning Meeting) or due to PK non-evaluability (as revealed during data analysis, based on the criteria specified below). Exclusion of a subject's data will be documented in the CTR.

Relevant protocol deviations may be

- *Incorrect trial medication taken, i.e. the subject received at least one dose of trial medication the subject was not assigned to*
- *Incorrect dose of trial medication taken*
- *Use of restricted medications*

Plasma concentrations and/or parameters of a subject will be considered as non-evaluatable, if for example

[figure not shown]
- *The subject experienced emesis that occurred at or before two times median t_{max} of the respective treatment (Median t_{max} is to be determined excluding the subjects experiencing emesis),*
- *The subject experiences emesis at any time during the labelled dosing interval.*
- *A predose concentration is $>5\% C_{max}$ value of that subject*
- *Missing samples/concentration data at important phases of PK disposition curve*

Plasma concentration data and parameters of a subject which is flagged for exclusion will be reported with its individual values but will not be included in the statistical analyses. Descriptive and inferential statistics of PK parameters will be based on the PKS.

The descriptive analysis of PK concentrations will be based on the ADS ADPC as described at the beginning of [Section 7](#).

Table 6.3: 1 Subject sets analysed

Class of endpoint	Subject set	
	TS	PKS
Analyses of PK endpoints		X
Safety parameters	X	
Demographic/baseline parameters	X	
Important protocol deviations	X	
Disposition	X	
Exposure	X	

6.5 POOLING OF CENTRES

This section is not applicable, because the study was performed in only one centre.

6.6 HANDLING OF MISSING DATA AND OUTLIERS

Handling of missing data and outliers will be performed as described in the CTP, Section 7.5.

The only exceptions where imputation might be necessary for safety evaluation are AE dates. Missing or incomplete AE dates are imputed according to BI standards (see BI-KMED-BDS-HTG-0035) [\(3\)](#).

Missing data and outliers of PK data are handled BI standards (see BI-KMED-TMCP-MAN-0012 [\(4\)](#) and BI-KMED-TMCP-MAN-0014 [\(5\)](#)).

6.7 BASELINE, TIME WINDOWS AND CALCULATED VISITS

The baseline value is defined as the last measurement before study drug administration in each treatment period. For laboratory data, baseline for both periods is the last measurement before study drug administration in the first period (-72:00).

Section 6.1 of the CTP: Study measurements and assessments scheduled to occur 'before' trial medication administration on Day 1 are to be performed and completed within a 3 h-period prior to the trial drug administration.

The acceptable deviation from the scheduled time for vital signs, ECG, and laboratory tests will be ± 15 min for the first 4 h after trial drug administration and ± 30 min thereafter. Starting from 48 h post-dose a deviation from the scheduled time for vital signs, ECG and laboratory tests of ± 120 min is acceptable.

Adherence to time windows will be checked via the consistency check listings at the RPM.

Unscheduled measurements of laboratory data and vital signs data will be assumed to be repeat measurements of the most recent scheduled measurement (e.g. for follow-up or confirmation of a particular value). Therefore, unscheduled measurements will be assigned to the planned time point of the previous scheduled measurement.

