## 1.4.3.6 Risk minimization (safety precautions and stopping rules)

The following risk minimization measures, including safety precautions and stopping rules, will be implemented in this study:

- Careful selection of the study dose, as described in Section 4.1.2.
- If dosing of several subjects is scheduled on a same day, subjects will be dosed at least 5 min apart.
- Application of the second single dose of BI 1595043 to each subject, only if the first single dose of BI 1595043 is safe, shows acceptable tolerability, and no stopping criterion is met (see Sections 3.3.4.1 and 3.3.4.3). At least 8 days will be maintained between the two drug administrations to each subject.
- A monitoring of safety laboratory with specific focus on plasma glucose levels and liver enzymes (see Flow Chart).
- Safety monitoring (including e.g. vital signs, 12-lead ECGs and adverse events) with a special focus on blood pressure and heart rate measurements.
- Ophthalmological examination at Screening and EoTrial Visit (see Section 5.2.3).

Page 30 of 75

Proprietary confidential information © 2021 Boehringer Ingelheim International GmbH or one or more of its affiliated companies

- Hospitalization of subjects at the trial site for at least 48 hours after study drug administration at each dose level. Based on the longest gMean terminal t_{1/2} in dose group 5 of up to 29.3 h (based on preliminary PK data) for BI 1595043 in this study, this is expected to cover the period of highest risk/ peak effect. During in house-confinement, subjects will be under medical observation and thoroughly monitored for both expected and unexpected adverse events.
- Exclusion of acetaminophen (paracetamol) as concomitant medication.
- Due to observed teratogenicity in rat, women will not be enrolled in this study.

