#### 4.1.2 Selection of doses in the trial

BI 1595043 dose selected in this trial is at the current predicted therapeutic dose of 30 mg (see Section 1.2.4).

BI 1595043 is a BCS class I compound with high permeability and high solubility. In SRD study (1445-0001), BI 1595043 was administered as oral solution and was rapidly absorbed with t_{max} of 0.75 or 1 hour, which is in line with BCS class I properties. In pre-clinical testing, tablet formulation had fast disintegration (1-3 min). Thus, no substantial difference in bioavailability is expected between oral solution and tablet formulation. Based on BCS class I properties, BI 1595043 exposures are expected to be minimally affected by food.

The selected dose of 30 mg is 3-fold lower than the maximum tested dose to date (90 mg) in the ongoing SRD study. At the dose of 30 mg,  $C_{max}$  is predicted to be 678 nM and  $AUC_{0-24}$  – 3,494 nM•h; these are about 3.7-fold and 3.3-fold lower, respectively, than the observed exposure after a single dose of 90 mg ( $C_{max}$  of 2,500 nM and  $AUC_{0-24}$  of 11,400 nM•h).

Overall, based on physical, chemical and PK properties, the exposure of 30 mg of BI 1595043 as tablet formulation under fed condition will unlikely exceed the observed exposure of 90 mg administered as oral solution in fasted state.

Page 39 of 75

Proprietary confidential information © 2021 Boehringer Ingelheim International GmbH or one or more of its affiliated companies

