	Albumin		X	X
	Albumin (Protein Electrophoresis)	X		
	Alpha-1-Globulin (Protein Electrophoresis)	X		
	Alpha-2-Globulin (Protein Electrophoresis)	X		
	Beta-Globulin (Protein Electrophoresis)	X		
	Gamma-Globulin (Protein Electrophoresis)	X		
	C-Reactive Protein (Quant)	X	X	X
	Uric Acid	X	X	X
	Cholesterol, total	X	X	X
	Triglyceride	X	X	X

Page 45 of 75

Proprietary confidential information © 2021 Boehringer Ingelheim International GmbH or one or more of its affiliated companies

Table 5.2.4.: 1 Routine laboratory tests (cont.)

Functional lab group	BI test name [comment/abbreviation]	A	В	С
Hormones	Thyroid Stimulating Hormone	X		
	Free T3 - Triiodothyronine	X		
	Free T4 – Thyroxine	X		
Electrolytes	Sodium	X	X	X
	Potassium	X	X	X
	Calcium	X	X	X
Urinalysis (Stix)	Urine Nitrite (qual)	X	X	X
	Urine Protein (qual)	X	X	X
	Urine Glucose (qual)	X	X	X
	Urine Ketone (qual)	X	X	X
	Urobilinogen (qual)	X	X	X
	Urine Bilirubin (qual)	X	X	X
	Urine RBC/Erythrocytes (qual)	X	X	X
	Urine WBC/Leucocytes (qual)	X	X	X
	Urine pH	X	X	X
Urine sediment	Only positive findings will be reported (for instance, the			
(microscopic	presence of sediment bacteria, casts in sediment, squamous			
examination if	epithelial cells, erythrocytes, leukocytes)			
erythrocytes,				
leukocytes nitrite or				
protein are abnormal				
in urine)				

A: parameters to be determined at Visit 1 (screening examination)

The tests listed in Table 5.2.4: 2 are exclusionary laboratory tests that may be repeated as required. The results will not be entered in the CRF/database and will not be reported in the CTR. Drug screening will be performed at screening and after admission to the trial site. Infectious serology will be performed at screening only.

B: parameters to be determined at Visit 1 on Day -3 to -1; and on Day 2 and Day 5 in each treatment period (i.e. at Visits 2 and 3) (for time points refer to Flow Chart)

C: parameters to be determined at Visit 4 (end of trial examination)

c34388550-04 Trial Protocol Page 46 of 75

Proprietary confidential information © 2021 Boehringer Ingelheim International GmbH or one or more of its affiliated companies

Table 5.2.4: 2 Exclusionary laboratory tests

Functional lab group	Test name
Drug screening (urine)	Amphetamine/MDA Barbiturates Benzodiazepine Cannabis Cocaine Methadone Methamphetamines/MDMA/XTC Opiates Tricyclic antidepressants

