#### • Hepatic injury

A hepatic injury is defined by the following alterations of hepatic laboratory parameters:

- o An elevation of AST (aspartate transaminase) and/or ALT (alanine transaminase) ≥3-fold ULN combined with an elevation of total bilirubin ≥2-fold ULN measured in the same blood sample, or
- o Aminotransferase (ALT, and/or AST) elevations ≥10 fold ULN

These lab findings constitute a hepatic injury alert and the subjects showing these lab abnormalities need to be followed up according to the 'DILI checklist' provided in the ISF. In case of clinical symptoms of hepatic injury (icterus, unexplained encephalopathy, unexplained coagulopathy, right upper quadrant abdominal pain,

c34388550-04 Trial Protocol Page 49 of 75

Proprietary confidential information © 2021 Boehringer Ingelheim International GmbH or one or more of its affiliated companies

etc.) without lab results (ALT, AST, total bilirubin) available, the Investigator should make sure that these parameters are analysed, if necessary in an unscheduled blood test. Should the results meet the criteria of hepatic injury alert, the procedures described in the DILI checklist should be followed.

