7.8.2 Laboratory data

The analyses of laboratory data will be descriptive in nature and will be based on BI standards [BI-KMED-BDS-HTG-0042] ([12](#)).

Laboratory data will be analysed qualitatively via comparison of laboratory data to their reference ranges. Values outside the reference range as well as values defined as possibly clinically significant will be flagged in the data listings.

Clinically relevant findings in laboratory data will be reported as baseline conditions (at screening) or as AEs (during the trial) if judged clinically relevant by the investigator, and will be analysed as such.

It is the investigator's responsibility to decide whether a lab value is clinically significantly abnormal or not (at the RPM at the latest).

Descriptive statistics of laboratory data including change from baseline will be calculated by planned time point based on the worst value of the subject at that planned time point (or assigned to that planned time point).

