7.8.3 Vital signs

Descriptive statistics over time including change from baseline will be performed for vital signs (blood pressure, pulse rate and body temperature). In the listing the difference from baseline will also be displayed.

For vital signs, descriptive statistics will be calculated by planned time point based on the last value of the subject at that planned time point (or assigned to that planned time point).

Clinically relevant findings in vital signs will be reported as AEs.

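### SAP 6.7 carries unscheduled lab and vital-sign values back past the dose, so an early post-dose value would be summarised in a pre-dose row

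*SAP*

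**What the plan says.** SAP 6.7 gives one rule for unscheduled laboratory and vital-sign values. Its premise is that "Unscheduled measurements of laboratory data and vital signs data will be assumed to be repeat measurements of the most recent scheduled measurement", and its consequence is "Therefore, unscheduled measurements will be assigned to the planned time point of the previous scheduled measurement". No exception is written for values taken after a dose. ECGs are not covered by the rule.

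The summary rules then bring the assigned values into the tables. Vital signs are summarised "based on the last value of the subject at that planned time point" (SAP 7.8.3) and laboratory data "based on the worst value of the subject at that planned time point" (SAP 7.8.2). Both sections state that values assigned to a time point count as belonging to it.

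Baseline is defined separately in SAP 6.7, as the final value obtained ahead of dosing in each period. For labs, the Period 1 pre-dose value serves both periods.

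**The concern.** A value taken after a dose cannot repeat one taken before it, yet the rule files it there whenever no planned measurement lies in between. The protocol also foresees a test that is not a repeat. If symptoms suggest hepatic injury and no liver results are available, "the Investigator should make sure that these parameters are analysed, if necessary in an unscheduled blood test" (Protocol 5.2.7.1.4).

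A row labelled pre-dose could therefore contain a post-dose value, and that value would be missing from every post-dose row. Protocol 1.4.3.6 plans safety monitoring "with a special focus on blood pressure and heart rate measurements", and Protocol 4.1.2 reports that the oral solution was "rapidly absorbed with t_{max} of 0.75 or 1 hour". The first hour after dosing, which has no planned vital signs before 1:00, can thus include the exposure peak.

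**Working it through.** There is no plan figure to reproduce. The check applies the SAP 6.7 rule to the planned schedule.

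**Inputs**
- Blood pressure and pulse (Flow Chart): -72:00 (Visit 2 only), -2:00, then 1, 2, 4, 8, 12, 24, 48, 72, 96, 120, 144 and 168 h.
- Safety labs (Flow Chart; note B to Protocol Table 5.2.4: 1): -72:00, then 24 h and 96 h of each period. Footnote 8 restricts the pre-dose lab to Visit 2, and footnote 5 limits admission testing to the drug screen and breath alcohol. Period 2 therefore has no planned pre-dose safety lab, which agrees with the single laboratory baseline in SAP 6.7.
- Washout: the minimum of 8 days, so the Period 2 dose falls at 8 × 24 = 192 h on a clock that starts at the first dose.

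**Rule:** assigned time = latest planned time at or before the actual time. Label error = actual time minus assigned time.

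| Value | Actual time after dose | Assigned to | Label error | Share of 168 h |
|---|---|---|---|---|
| BP, pulse, either period | 0 to 1 h | -2:00, same period | 0-(-2) = 2 h to 1-(-2) = 3 h | 60/10080 min = 0.6% |
| Lab, Period 1 | 0 to 24 h | -72:00 | 0-(-72) = 72 h to 24-(-72) = 96 h | 1440/10080 min = 14.3% |
| Lab, Period 2 | 0 to 24 h | Period 1, 96 h | 192-96 = 96 h to 216-96 = 120 h | 1440/10080 min = 14.3% |

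Spot checks: vital signs at 0.25, 0.5, 0.75 and 0.99 h all map to -2:00, while one at 1.5 h maps correctly to 1:00. Period 1 labs at 0.5 to 23.9 h map to -72:00, and one at 30 h maps to 24 h.

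Two variations matter. If the Visit 2 ambulatory visit is omitted, as footnote 8 allows, the Period 1 lab goes back to screening. If a -72:00 lab were nevertheless taken in Period 2, the Period 2 lab would go to that pre-dose row instead of to Period 1.

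**Which value the row shows.** For vital signs the last value is used, so the displaced post-dose reading replaces the true pre-dose one. For labs the worst value is used, so the displaced value enters only if it is the worst one filed there.

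**Effect on a row mean.** One displaced vital sign that differs by *d* from the true pre-dose reading shifts the mean by *d/n*. The size of *d* is assumed (10 to 20 mmHg), because the documents give none.
- *n* = 14: 10/14 = 0.71 and 20/14 = 1.43 mmHg.
- *n* = 12 (two non-completers): 10/12 = 0.83 and 20/12 = 1.67 mmHg.

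**Treatment label in Period 2.** Protocol 7.3.4 assigns a measurement to treatment through its planned time. If the assigned time is used for that purpose, a Period 2 lab would be tabulated under the other treatment. SAP 6.7 does not mention treatment, and SAP 6.1 refers treatment handling to a technical plan that is not available, so this consequence is conditional.

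**The case against.** The convention is prespecified, and it suits most extra tests: Protocol 5.2.4 itself speaks of retests at the investigator's discretion. The one non-repeat test in the protocol would need hepatic symptoms within 24 h of a single dose, before the scheduled 24 h lab, and no comparable example exists for vital signs in the first hour. The planned 1:00 reading already samples close to the peak. SAP 7.8.2 also relies on an internal laboratory standard that may contain a safeguard.

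Other routes keep the information. Clinically relevant changes become adverse events, which are assigned by actual dosing time. Individual values are listed, out-of-range labs are flagged, and the vital-signs listing shows the difference from baseline. The 60-minute gap is nominal: with the permitted ±15 min at the 1:00 reading it is 45 to 75 min.

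Much of this stands. The number of affected values is unknown and may be zero, the shares above are shares of clock time and not rates of occurrence, and the wrong-treatment case cannot be asserted outright. An unseen standard could also prevent the error. But no available document states such a safeguard, and the SAP text followed as written gives the wrong row. Listings and adverse-event reporting limit the consequence without correcting the table.

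**Conclusion.** The concern holds as a minor error in a stated rule. For an unscheduled value taken between a dose and the first planned post-dose measurement, SAP 6.7 gives a time label that is wrong by 2 to 3 h for blood pressure and pulse, 72 to 96 h for Period 1 labs, and 96 to 120 h for Period 2 labs at the minimum washout (more if the washout is longer). The effect is confined to descriptive by-time-point safety rows and arises only if such values occur. Baseline is not claimed to be wrong, because its definition rests on values obtained before dosing. The PK endpoints and adverse-event analyses are unaffected.

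The conclusion assumes that the planned times are as read from the Flow Chart, that Period 2 has no pre-dose safety lab, and that no unseen internal standard overrides the SAP text.

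**What to change.** Add to SAP 6.7:

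> An unscheduled measurement is never assigned to a time point before the most recent study drug administration. A value taken after a dose and before the first scheduled post-dose point is shown as an unscheduled post-dose value under the treatment just given and does not enter any pre-dose row.

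The second sentence also settles the treatment label for Period 2 labs. The cost is two sentences and one programming check of actual measurement time against dosing time. No new data are needed, and the PK and adverse-event analyses do not change. If the technical plan or laboratory standard already works this way, the SAP only needs to say so.

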7. PLANNED ANALYSIS

Safety analysis (refer to [Section 7.8](#)) will be performed by [REDACTED] and will be presented in Sections 15.1 to 15.4 of the CTR and in Appendix 16.2 and 16.1.13.1.

Inferential statistical analyses of PK endpoints (refer to [Section 7.4](#) and [Section 7.5.2](#)) will also be performed by [REDACTED] and will be presented in Section 15.5 of the CTR and in Appendix 16.1.13.3.

Descriptive data analysis of PK endpoints and concentrations will be performed by the [REDACTED] at [REDACTED] and will be presented in Section 15.6 of the CTR.

The format of the listings and tables will follow the BI standards (see BI-KMED-BDS-HTG-0045 ([6](#)) with the exception of those generated for PK-calculations following BI standards for PK/PD analysis ([7](#)).

The individual values of all subjects will be listed, sorted by treatment sequence, subject number and visit. The listings will be included in Appendix 16.2 of the CTR.

For End-Of-Text (EoT) tables, the set of summary statistics is:

N	number non-missing observations
Mean	arithmetic mean
SD	standard deviation
Min	minimum
Median	median
Max	maximum

For analyte concentrations, the following descriptive statistics will additionally be calculated:

CV	arithmetic coefficient of variation
gMean	geometric mean
gCV	geometric coefficient of variation

For PK parameters, the following descriptive statistics will additionally be calculated:

CV	arithmetic coefficient of variation
gMean	geometric mean
gCV	geometric coefficient of variation
P10	10th percentile
Q1	1st quartile
Q3	3rd quartile
P90	90th percentile

The data format for descriptive statistics of concentrations will be identical to the data format of the respective concentrations. The descriptive statistics of PK parameters will be calculated

using the individual values with the number of decimal places as provided by the evaluation program. Then the individual values as well as the descriptive statistics will be reported with three significant digits in the CTR.

Tabulations of frequencies for categorical data will include all possible categories and will display the number of observations in a category as well as the percentage (%) relative to the respective treatment group (unless otherwise specified, all subjects in the respective subject set whether they have non-missing values or not).

The precision for percentages should be one decimal point, unless the denominator is smaller than 100 (in all treatment columns), in which case percentages are given in integer numbers. The category missing will be displayed only if there are actually missing values.

Exclusion of PK parameters

The ADS “ADPP” (PK parameters) contains column variables APEXC and APEXCO indicating inclusion/exclusion (APEXC) of a PK parameter and an analysis flag comment (APEXCO). All analyses based on the PKS will include parameters if they are not flagged for exclusion, that is APEXC is equal to “Included”.

Exclusion of PK concentrations

The ADS “ADPC” (PK concentrations per time-point or per time-interval) contains column variables ACEXC and ACEXCO indicating inclusion/exclusion (ACEXC) of a concentration and an analysis flag comment (ACEXCO). Exclusion of a concentration depends on the analysis flag comment ACEXCO. For example, if ACEXCO is set to ‘ALL CALC’, the value will be excluded for all types of analyses based on concentrations. If ACEXCO is set to ‘DESC STATS’ the value will be excluded from descriptive evaluations per planned time point/time interval. If ACEXCO contains the addition ‘TIME VIOLATION’ or ‘TIME DEVIATION’ the value can be used for further analyses based on actual times. If ACEXCO is set to ‘HALF LIFE’, the value will be excluded from half-life calculation (and, as a consequence, any calculation that relies on λ_z) only; the value is included for all other analyses.

Further details are given in *BI-KMED-TMCP-MAN-0014* “Noncompartmental Pharmacokinetic / Pharmacodynamic Analyses of Clinical Studies” ([5](#)) and *BI-KMED-TMCP-MAN-0010*: “Description of Analytical Transfer Files and PK/PD Data Files” ([8](#)).

